7.2. Pre-Screening / Screening (Day -14 to Day 0)

PRE-SCREENING: will be performed by research coordinator, either by phone or in person, following verbal consent from the participant. Information obtained will include self-reported information relevant to inclusion and exclusion criteria (to be confirmed by objective assessment during screening).

SCREENING* (Day -14 to Day 1):

**Sequence of screening procedures not pre-defined after informed consent and HIPAA authorization are obtained.*

Informed Consent and HIPAA Authorization

To be obtained by PI or Study Coordinator prior to any other procedures listed herein.

Demographic/Medical History

Medical history will be collected via a checklist completed by the subject. Age, race, and ethnic origin will be recorded. The diagnosis of PPD will be determined using the SCID-5. Subjects will be specifically asked about the following: depression, anxiety, and other diagnoses per DSM-5. Pregnancy history (including number of pregnancies, number of births, methods of delivery, and birth complications) and PPD episodes will be recorded.

Vital Signs

Vital signs include oral temperature (°C), respiratory rate, heart rate, and blood pressure. Heart rate and blood pressure to be collected in supine position at all scheduled time points as well as in the standing position at specific time points listed in Table 3.

Weight, Height and Body Mass Index

Body weight and height will be measured; body mass index will be programmatically calculated in the study record.

Physical Examination

Physical examinations of major body systems will be undertaken and recorded. Major body systems to be included in the screening physical examination are head, eye, ear, nose and throat, heart, lungs, abdomen, and extremities; as well, cognitive, neurological, and mental status examinations will be performed.

Electrocardiogram

Twelve-lead ECGs will be performed. The Investigator will record if the ECG is normal; abnormal, not clinically significant; or abnormal, clinically significant (CS). If abnormal, details of the abnormality will be provided (e.g., first-degree AV block, bundle branch block). The standard intervals (heart rate, PR, QRS, QT, and QTcF) will be recorded for all ECGs.

Laboratory Assessments

Blood samples will be collected for hematology, serum chemistry, and coagulation. Analytes to be evaluated are summarized in Table 4.

All blood samples, including those taken for eligibility screening, will be sent to the central laboratory. Laboratory assessments obtained by outside medical clinic will be considered valid if collected within 30 days of infusion start date.

Table 4: Summary of Laboratory Analytes

Hematology	complete blood count (red blood cells, white blood cells with differentiation and absolute values, hemoglobin, hematocrit, reticulocytes, and platelets)
Coagulation (at Screening only)	activated partial thromboplastin time, prothrombin time, and international normalized ratio
Biochemistry	serum electrolytes (sodium, potassium, chloride, bicarbonate or total carbon dioxide, calcium, and phosphorus) renal function tests (creatinine and blood urea nitrogen); liver function tests (total bilirubin, alkaline phosphatase, aspartate aminotransferase, alanine aminotransferase, and gamma glutamyl transferase); thyroid stimulating hormone; total protein; albumin and glucose (fasting or non-fasting)

All clinical laboratory test results outside the reference range will be interpreted by the Investigator as abnormal, not clinically significant; or abnormal, CS. Screening results considered abnormal, and CS at the Screening Visit may make the subject ineligible for the study pending review by the Investigator. Clinically significant abnormal results after screening will be considered and reported as AEs.

Pregnancy Test

All subjects will be tested for pregnancy by serum or urine human chorionic gonadotropin at the during screening.

Drugs of Abuse and Alcohol

Urine assessment for select drugs of abuse will be performed (including amphetamines, barbiturates, benzodiazepines, cannabinoids, cocaine, opiates, and phencyclidine). A positive urine drug screen is exclusionary, unless deemed by the investigator to reflect a prescribed medication. Alcohol will be assessed via breathalyzer or urine dipstick.

Hormones and Biochemistry

Blood samples will be collected and may be analyzed for estrogen, progesterone, progesterone metabolites, thyroid function (TSH, T4, T3), and markers of inflammation.

Columbia-Suicide Severity Rating Scale

Suicidality will be monitored during the study using the C-SSRS (Posner 2011). This scale consists of a baseline evaluation that assesses the lifetime experience of the subject with suicidal ideation and behavior, and a post-baseline evaluation that focuses on suicidality since the last study visit. The C-SSRS includes 'yes' or 'no' responses for assessment of suicidal ideation and behavior as well as numeric ratings for severity of ideation, if present (from 1 to 5, with 5 being the most severe).

The "Baseline/Screening" C-SSRS form will be completed at screening (lifetime history and past 24 months). The "Since Last Visit" C-SSRS form will be completed at all subsequent time points, as outlined in Table 1.

Hamilton Depression Rating Scale

The HAM-D will be administered by PI or Study Coordinator at screening to confirm eligibility based on a score of ≥ 20 , which was the threshold used in the original BRX clinical trials.

Structured Clinical Interview for DSM-V Disorders

The SCID-V will be administered by PI or Study Coordinator at screening to confirm eligibility based on diagnosis of Major Depressive Disorder with Peripartum Onset. The SCID-V will also be used to diagnose and record concurrent anxiety disorders, and to rule out current suicide attempt, concurrent alcohol and/or substance use disorder, and history of psychosis or mania.

7.3. Enrollment / Baseline (Day 0)

Refer to Tables 1 and 3 for schedule of procedures at Baseline. Procedures to be performed by the following personnel: PI, Study Coordinator, Research Nurse, and/or EEG technician.

Baseline (Hour 0)

- Subject will be admitted to UNC Hospital on a Monday or Tuesday morning. Prior to administration of drug intervention, the subject will undergo the following procedures:
 - Measure subject's height and weight, record, and submit to IDS to calculate drug dosage
 - Negative drug/alcohol and pregnancy test (if positive, subject will be withdrawn from the study)
 - Baseline blood sample to measure circulating allopregnanolone levels
 - Vital signs
 - Review of current concomitant medications and nonpharmacological interventions
- **First EEG recording:**

- EEG cap will be fitted by technician and electrodes filled with gel solution. Impedance will be measured to ensure proper adherence to scalp. Cap set-up will take approximately 20 minutes.
- Recording of 8-minute resting state EEG, eyes alternating open and closed at regular intervals.
- Cap will remain on the subject until the end of the Hour 8 session, so as not to disrupt the electrode placement over the course of the serial recordings. EEG will be recorded for 8-minute sessions at Hours 4 and 8 on Day 1 (not continuously throughout the day).
- **Self-Report measures:** Electronic versions of the following surveys will be administered: C-SSRS, EPDS; STAI (Y1&Y2); SCS; BIMF; IDS-SR; RRS-10; SHAPS.
- **Semi-Structured interview & iMotions Recording:** Facing a laptop equipped with a standard camera and microphone and iMotions Affectiva software, the subject will be administered a semi-structured interview about depressive symptoms and affect by study personnel. Interview questions will include the HAM-D and additional questions to assess the subject's experiences of enjoyment, guilt, and irritability. The interview and recording will last 10-20 minutes. A memory probe task will be completed, in which a subject will be asked to think of a sad event in her life and focus on that memory for 30 seconds while the laptop camera records her facial expressions. Then they will be asked to rate their emotional experience during that recall. This procedure will be repeated with a prompt to recall a happy memory from her life. Subjects will then be asked to come up with a word or phrase that can be used to recall each event during later recording sessions.
- **Heart Rate Variability:** Using a non-invasive device, heart rate variability data will be collected throughout the infusion. The device will be adhered to the subject's torso by two electrodes and will begin collecting data once it is adhered to the skin. The device will be removed following completion of the brexanolone infusion

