3.1. Specific Aim

To Evaluate the feasibility of obtaining serial EEG recordings and affective state measures in women with PPD who receive inpatient BRX infusion treatment.

3.2.Exploratory Aims

Exploratory Aim 1

To calculate resting state nodal flexibility from five serial EEG recordings.

Exploratory Aim 2

To identify rapid brain state configurations and their probability density function from five serial EEG recordings.

Exploratory Aim 3

To assess the ability of iMotions Affectiva software to identify affective states using facial expression recognition analysis.

Exploratory Aim 4

To assess the amplitude of left frontal midline theta oscillations by performing spectral analyses of data collected from five serial EEG recordings.

4. Study Design

This is a feasibility study of performing repeated EEG recordings and assessments of affective states during open-label administration of BRX to women with postpartum depression. Study phases will include screening, enrollment, intervention, and follow-up. Subjects will be screened for eligibility criteria through clinical assessments and self-report. Enrolled subjects will be admitted to the UNC Women's Hospital, where five serial EEG recordings will be obtained, along with frequent assessments of affective state, before, during, and after a 60-hour IV infusion of BRX. Follow-up procedures will occur 30 days after completion of the drug infusion, and will include assessments of PPD and affective symptoms, as well as an exit interview with the PI. If feasibility outcomes are achieved, exploratory EEG analyses will be performed with AMICA (adaptive mixture independent component analysis), community detection, and microstate assessment. Exploratory analyses of data collected by facial expression detection software (iMotions Affectiva) are also planned.

4.1.Treatment Design

Based on an FDA-approved regimen, the 60-hour infusion will be administered as follows: 30 mcg/kg/hour (Hour 0 to 4), then 60 mcg/kg/hour (Hour 4 to 24), then 90 mcg/kg/hour (Hour 24 to 52), followed by 60 mcg/kg/hour (Hour 52 to 56), and 30 mcg/kg/hour (Hour 56 to 60). A programmable peristaltic infusion pump will be used to ensure accurate delivery of BRX.

4.2.Experimental / Observational Design

All enrolled participants receive the same intervention.

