7.1. Table of Events

Table 3: Schedule of Events

Study Procedure	Screening Period	Treatment Period/Inpatient Stay (Day 1 to Day 4)						Follow-up
		D-14 to 1	D1	D1	D1	D2	D3	
Visit Days		H0*	H4	H8	H28	H60	H72	D30 (±3d)
Hour								
Informed Consent	X							
SCID-5	X							
Demographics	X							
Medical History	X							
Height		X						
Body Weight		X						
Physical Examination ^a	X							
Drug and Alcohol Test ^b	X	X						
Pregnancy Test ^c	X	X						
Clinical lab assessments ^d	X							
ALLO blood sample ^e		X			X		X	
12-lead ECG ^f	X							
Vital Signs ^g	X	X	q4h (while awake) during infusion				X	
C-SSRS ^h	X	X					X	
HAM-D ⁱ	X	X	q4h (while awake) during infusion				X	X
SMDDS ⁱ		X	q4h (while awake) during infusion				X	X
EPDS ⁱ		X	q4h (while awake) during infusion				X	X
STAI (state Y-1) ⁱ		X	q4h (while awake) during infusion				X	X
SCS ⁱ		X	Q4h (while awake) during infusion				X	X
BIMF ⁱ		X					X	X
IDS-SR ⁱ		X					X	X
RRS-10 ⁱ		X					X	X
SHAPS ⁱ		X					X	X
STAI (trait Y-2) ⁱ		X					X	X
EEG Recording ⁱ		X	X	X	X		X	
RS Eyes Open/Closed (8min) ^{i,j}		X	X	X	X		X	

iMotion Recording ^{i,j}		X	X	X	X		X	
Semi-structured Interview ^{i,k}		X	X	X	X		X	
Brexanolone infusion				X				
Continuous pulse oximetry ^l				X				
Continuous HRV collection				X				
Adverse Events				q2h (while awake) during infusion		X	X	
Monitor for excessive sedation				q2h (while awake) during infusion				
Prior/Concomitant medications ^m	X	X				X	X	
Nonpharmacological interventions ⁿ	X	X				X	X	
Exit Interview								X
Compensation (total \$750)	\$50	\$100	\$100	\$100	\$100		\$100	\$200

AE= adverse event; ALLO= allopregnanolone; BIMF= Barkin Index of Maternal Functioning; C-SSRS = Columbia-Suicide Severity Rating Scale; D= Day; ECG= electrocardiogram; EEG= electroencephalogram; EPDS= Edinburgh Postnatal Depression Scale; HAM-D= Hamilton Depression Rating Scale; H=Hour; IDS-SR= Inventory of Depression Symptoms Self-Report; Q= every; RRS-10= Ruminative Responses Scale-10; RS= Resting State; SCID-5= Structured Clinical Interview for Diagnostic and Statistical Manual of Mental Disorders, Fifth Edition; SCS= State Complacency Scale; SHAPS= Snaith-Hamilton Pleasure Scale; SMDDS= Symptoms of Major Depressive Disorder Scale; STAI= State-Trait Anxiety Inventory;

* = All H0 procedures to be completed prior to dosing

a Full physical examination at screening. Symptom-directed physical examination may be conducted at subsequent time point

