7.4. Study Visits (Days 1-4)

Refer to Tables 1 and 3 for schedule of procedures at study visits following Baseline. Procedures to be performed by the following personnel: PI, Study Coordinator, Research Nurse, and/or EEG technician.

Hour 4 Visit

- **Second EEG recording:** With the cap in place from the baseline recording, electrode impedance will be measured, and electrode gel refilled to ensure proper fit. A second EEG will be recorded during an 8-minute resting state with eyes opened and closed at regular intervals. The cap will remain on the subject until the end of the Hour 8 recording but will not be recording continuously between sessions.
- **Self-Report measures:** Electronic versions of the following surveys will be administered: SMDDS, EPDS, STAI (Y1), and SCS.

- **Semi-Structure interview & iMotions Recording:** Facing a laptop equipped with a standard camera and microphone and iMotions Affectiva software, the subject will be administered a semi-structured interview about depressive symptoms and affect by study personnel. Interview questions will include a modified version of the HAM-D (items suitable for repeated measure within the same day) and additional questions to assess the subject's experiences of enjoyment, guilt, and irritability. The interview and recording will last 10-20 minutes. The memory probe task will be completed, in which a subject will be told the predetermined word or phrase to cue recall of the sad and happy events, while the camera records her facial expressions for 30 seconds for each event and the subject rates her emotional experience.

Hour 8 Visit

- **Third EEG recording:** With the cap in place from the Hour 4 recording, electrode impedance will be measured, and electrode gel refilled to ensure proper fit. A third EEG will be recorded during an 8-minute resting state with eyes opened and closed at regular intervals. Following completion of this recording, the cap will be removed.
- **Self-Report measures:** Electronic versions of the following surveys will be administered: SMDDDS, EPDS, STAI (Y1), and SCS.

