Exploratory Aim 3: To assess the ability of the iMotions Affectiva software to identify differences in affective state (determined by symptom ratings). Our previous data demonstrate delayed self-recognition of change in affective state, which suggests that affect state changes occur and manifest (to others) prior to a subject's labeling (and recognizing) the state change as having occurred. Affectiva is a software that permits detection of emotion in facial expression by examining and integrating key alterations in facial musculature. The software calculates emotion scores, or the percent time spent in a certain affective state, as the weighted average of action units (tiny musculature changes). We will display in tabular form the emotion scores during the affective probe in each session across all five time points and will plot the percentage of time spent in each affective state against the HAM-D ratings and responses to the semi-structured interview.

Exploratory Aim 4: To assess the amplitude of left frontal midline theta oscillations by performing spectral analyses of data collected from five serial EEG recordings. Fast Fourier transform will be applied to each two-second EEG epoch, and the average spectral power will be calculated within the canonical theta frequency band from 4 to 7 Hz. To estimate frontal midline theta (FMT), theta power in electrode FCz will be log-transformed and then normalized for each participant using the z-transformation across the 90 scalp data channels. Point estimates and CI will be presented in tabular form.

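### In the memory-probe clips, the only pre-dose recording is uncued first-time recall and the four later ones are cued, so changes from Hour 0 mix recall procedure with post-dose change (minor)

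*Combined protocol and SAP*

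**What the plan says.** **Hour 0 (section 7.3).** During the memory probe "a subject will be asked to think of a sad event in her life and focus on that memory for 30 seconds", filmed by the laptop camera. She then rates the experience, and the same is done for a happy memory. The cue comes last, for use at the later sessions: "Subjects will then be asked to come up with a word or phrase that can be used to recall each event".

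**Hours 4, 8 and 28 (section 7.4) and Hour 72 (section 7.6).** The wording is the same at all four sessions: "a subject will be told the predetermined word or phrase to cue recall of the sad and happy events". Each event is again filmed for 30 seconds and rated.

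**Timing and arms.** The footnote to Table 3 reads "All H0 procedures to be completed prior to dosing", so Hour 0 is the one probe recorded before the drug. Section 4.2 states "All enrolled participants receive the same intervention", so there is no comparison group.

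**Analysis.** For Exploratory Aim 3, section 9.3 says: "We will display in tabular form the emotion scores during the affective probe in each session across all five time points". It also plots time in each affective state against HAM-D and the interview responses. Table 1 adds that changes in facial expression are meant to help detect alterations in affective state caused by brexanolone. Section 9.3 does not mention that the recall procedure differs at Hour 0.

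**The other facial stimulus.** The same software records a semi-structured interview of 10 to 20 minutes at all five sessions, with questions on enjoyment, guilt and irritability each time. Table 1 describes this interview as standing in for an affective probe. The memory probe itself appears in neither Table 1 nor Table 3.

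**The concern.** The Hour 0 clip shows a woman choosing a memory and recalling it for the first time in the study. The four later clips show her returning to an event already chosen, prompted by her own phrase. If cueing or prior selection alters how much, or how soon, emotion shows on the face, a change from Hour 0 contains that alteration as well as anything the infusion did.

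With one pre-dose session and one arm, nothing in the data separates the two. A larger sample would not help, because this is an offset in the comparison and not sampling noise. At stake is how the five-session table of emotion scores is read. The step from Hour 0 to Hour 4 matters most. Section 9.3 motivates the aim by suggesting that affect may change visibly before the woman recognises it, and that step is where the procedure switches.

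**Working it through.** The plan gives no effect size, SD or target for the facial outcomes, so there is no figure of its own to reproduce. The check is whether the design can separate the recall procedure from the post-dose change.

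**Inputs** (sections 7.3, 7.4 and 7.6, Table 3):

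| Session | After start of infusion | Recall cued by the phrase |
|---|---|---|
| Hour 0 | 0 | 0 |
| Hour 4 | 1 | 1 |
| Hour 8 | 1 | 1 |
| Hour 28 | 1 | 1 |
| Hour 72 | 1 | 1 |

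**Step 1: identifiability.** The two indicator columns are both (0, 1, 1, 1, 1), with correlation 1. A design matrix with an intercept and these two columns has rank 2, not 3. The cueing effect and the post-dose effect cannot both be estimated.

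**Step 2: what each contrast contains.** Let δ_j be the drug effect at session j, ρ_j the combined effect of time, repetition and hospital stay, and τ the effect of cued versus first-time recall. Assume that these add and that τ is the same at every cued session.

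- Later session minus Hour 0: δ_j + ρ_j + τ.
- One later session minus another: (δ_j − δ_k) + (ρ_j − ρ_k). Here τ cancels.

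**Step 3: count.** Five sessions give 5 × 4 / 2 = 10 pairwise contrasts. Four involve Hour 0 (0–4, 0–8, 0–28, 0–72) and carry τ. The other 4 × 3 / 2 = 6 do not.

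**Step 4: the interview recordings.** The interview has no cue phrase at any session, so none of its 10 contrasts carries τ. Its content does vary in another way: section 7.4 uses a modified HAM-D at Hours 4 and 8, while Hours 0, 28 and 72 use the full one. That is a separate matter.

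**Step 5: effect of the remedy.** If Hour 0 is also cued, the cue column becomes (1, 1, 1, 1, 1), which is the intercept, and τ cancels from all 10 contrasts. The ρ terms remain.

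**The case against.** The case against giving this much weight is strong in several respects.

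- **Other facial data are clean.** A reader might infer that every pre-to-post change in facial response is affected. The documents do not support that. The interview recordings run at all five sessions without the switch, and the memory probe is two 30-second clips beside them.
- **The link to the analysis is uncertain.** Section 9.3 does not define *affective probe*. It also uses the term for EEG measures in Exploratory Aims 1 and 2, although the scheduled EEG is resting state only. The amendment log records that an affective Stroop task/probe was removed, so the term may be left over. The memory probe is the natural reading, because it is the only procedure in sections 7.3 to 7.6 called a probe and section 9.3 mentions the interview separately. It is still a reading.
- **No pre-to-post facial contrast is named.** Aim 3 asks whether the software tracks affective state as rated. Section 9.1 gives nodal flexibility, spectral power and symptom scales as examples for pre/post differences. That list is only illustrative, and Table 1 does speak of detecting drug-induced change, so the concern survives in reduced form.
- **Much is held constant.** The events, the 30-second window, the camera and the rating step are common to all sessions. The phrase is described as predetermined; no practice run appears, so calling it rehearsed goes beyond the text.

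A reader might also infer a direction: search time lowers expression at Hour 0, so reactivity seems to rise under the drug. Suppose 3 to 10 seconds of neutral-faced search and 40% true time in the target emotion. The artefact would be 0.40 × 3/30 = 4 to 0.40 × 10/30 = 13.3 percentage points. All of these inputs are assumptions. Section 7.3 does not say whether the 30 seconds start at the prompt or once a memory is in mind. In the second case search time, and this artefact, is zero. A first recall could also be more expressive than a repeated one, which would reverse the sign.

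**Conclusion.** The concern holds for the memory-probe clips. All four changes from Hour 0 are fully aliased with the switch from first-time, self-selected recall to cued recall, and no analysis can undo this because no cued clip exists before dosing. The six contrasts among Hours 4, 8, 28 and 72 are free of it.

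The size and sign of τ are unknown, and nothing in the documents bounds them. The consequence is confined to an exploratory, descriptive display, and it depends on *affective probe* in section 9.3 meaning the memory probe. The three primary feasibility outcomes are untouched. Removing the switch would not isolate a drug effect either, since time, repetition and hospitalisation remain mixed with drug in a single arm. Severity is minor; the point is worth making because the confound is avoidable at almost no cost.

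**What to change.** 1. In section 7.3, have the woman choose both events and both cue phrases before the camera starts. Then record the Hour 0 probe before dosing, with the same spoken cue and the same start point for the 30 seconds as at Hours 4, 8, 28 and 72. Use that clip as the baseline.
2. In sections 7.3, 7.4 and 7.6, state when the 30 seconds begin.
3. In section 9.3, state that *affective probe* for Exploratory Aim 3 means this memory probe, or name the stimulus that is meant. List the memory probe in Tables 1 and 3.
4. For any woman already recorded in the present order, mark her Hour 0 clip as uncued in the displays and note the limitation.

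The cost is a reordering of two steps at Hour 0 and a few lines of text. No staff, visit or procedure is added.
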